19.4 MAINTAINING RECORDS	
19.5 RECORD RETENTION	. 39
19.6 INVESTIGATIONAL PRODUCT ACCOUNTABILITY	. 39

19.7 STUDY CLOSEOUT	39
19.8 AUDITS AND INSPECTIONS	39
19.9 ANNUAL, INTERIM AND FINAL REPORT	40
20. STATISTICAL METHODOLOGY AND ANALYSIS	40
20.1 ANALYSIS POPULATIONS	40
20.2 DISPOSITION OF SUBJECTS	40
20.3 DEMOGRAPHIC AND OTHER SUBJECT CHARACTERISTICS	40
20.4 EXTENT OF EXPOSURE	40
20.5 PRE-TRIAL AND CONCOMITANT MEDICATIONS	40
20.6 PRIMARY OUTCOME	41
20.7 SAFETY AND OTHER OUTCOME MEASURES	41
20.8 MONITORING OF SAFETY AND PREGNANCY	42
APPENDIX 1. INVESTIGATOR RESPONSIBILITIES	43

REVISION HISTORY

Version	Date Justification for Revision							
1.0	01 Aug 2014	Initial version						
2.0	14 Jan 2015	Revise Contact Information, format issues, version issues						
3.0	17 Feb 2015	Revised in accordance with FDA recommendations						
4.0	9 July 2015	Revised various sections within the protocol to reflect outcome of clinical investigators meeting.						
5.0	19 September 2017	Added subject contact at the end of each 28-day cycle post the 52 Week visit. Added statistical analysis information. Separated out the post 52 week thru Year 3/Exit for more clarity. Updated the potential risks / adverse events with PhII 1-year data. Removed appendix 2, ICF template.						

INVESTIGATIONAL PLAN SUMMARY

Title: Evaluation of the Effectiveness, Safety and Tolerability of the

ContraMed VeraCept Intrauterine Copper Contraceptive for

Long-Acting Reversible Contraception

Protocol #: CMDOC-0008

Version 5.0 / 19 September 2017

Device Name: VeraCept Intrauterine Copper Contraceptive (referred to as

VeraCept or Study Device throughout this document)

Study Design: Prospective, multi-center, single-arm, open-label, Phase II clinical

study

Study Purpose: To evaluate the effectiveness, device placement, safety, and

tolerability of VeraCept to support commencing a Phase III

Clinical Study

Study Duration: Subject enrollment will take approximately 4 months. Each

subject will be followed for 12 months after device placement for the protocol endpoints, and then every 6 months thereafter for

those subjects who wish to continue study device use

Enrollment: Up to 250 subjects will be consented, screened and have

VeraCept placed, with a goal to have 2240 evaluable cycles at 12 months. It is planned that 225 of the 250 subjects will be within the 18-35 year age range, with a total of 2015 evaluable cycles. The remaining 25 subjects will be within the 36-40 year age

range.

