## 3.1.2 Analysis of 1-Year data

An analysis of the 1-year data was performed after all the subjects are enrolled and all the 1-year data were collected, monitored, and cleaned. All outputs in Section 5.2 that involve 1-year data were created since this analysis was the final analysis of the 1-year data. The analysis of 1-year data was the main analysis for the study. Secondarily, an analysis will be done at the end of the study to include all 3-year data.

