## 3.7.2 Efficacy Analyses for the Whole Study

Post-Year 1 sexual activity and contraceptive use information can be found in the Cycle Contact CRF, which was added since the Extension study (Year 2) started, i.e., this CRF wasn't present from the beginning of the study, but added as a mid-study change. Each record in this form is for one cycle and has the following 2 key questions for determining if a cycle is pregnancy-risk or not:

- Did the subject have intercourse at least once during the cycle? (Yes, No)
- Did the subject use backup contraception during the cycle? (Yes, No)

If the answer is "Yes" to the first question and "No" to the second question, or the subject was pregnant within a cycle (determined form the Pregnancy Test form), that cycle will be considered as a pregnancy-risk cycle; otherwise, the cycle will not be considered as a pregnancy-risk cycle.

For cycles without any Cycle Contact information, e.g., neither of the above 2 "Yes"/"No" questions were answered and a subject wasn't pregnant within the cycle either, the following procedure will be used to do the estimate for the subject:

- A. find the total number of such type of cycles for that subject
- B. find proportion of pregnancy-risk cycles from Year 1 diary data of the subject, which will be calculated as the number of pregnancy-risk cycles divided by the total number of cycles from Diary CRF
- C. The number from Step A is multiplied by the number from Step B, and then rounded to 1 decimal place, which will be the estimated number of pregnancy-risk cycles where Cycle Contact information is missing for the subject.

The number from Step C will be added to the number of pregnancy-risk cycles from those without missing Cycle Contact information, and then added to the Year 1 pregnancy-risk cycles from Diary CRF data to get denominator value of the Pearl Index for Year 2 (data cut off at 26 cycles) and Year 3 (data cut off at 39 cycles). The numerator will be the number of on-treatment pregnancies by the end of Cycle 26 and Cycle 39, respectively.

The Year 2 and Year 3 analyses will also be performed without inclusion of cycles with missing Cycle Contact information, i.e., not doing estimates of pregnancy-risk through the above Steps A, B, and C.

The 95% Confidence Intervals for the Pearl Index will be calculated, by using the formula in the above Section 3.7.1, at the following 3 scenarios:

- All EP subjects
- EP subjects with at least one live birth

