## 3.8.10 Long Term Follow Up Visits

Long term follow-up office visits for additional 2 years will occur every 6 months for those subjects who continue study device use after 1 year (52 weeks). In addition to vital signs, physical exam, pelvic exam, etc., as those shown in Section 5.1 "Study Schedule of Assessments", the assessments also include the following 3 questions which will be summarized categorically with number and percentage of subjects provided for each answer.

- Did you have vaginal intercourse at least once since your last visit? (Yes, No)
- Did you use any additional birth control methods in the past 6 months? (Yes, No)
- How often has the subject had vaginal intercourse in the past 6 months? (Not Once, Once a month or less, Several Times a Month, Once or Twice a week, Several Times a week, At least once a day)

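### The fill for extension cycles without Cycle Contact data ignores the 6-month follow-up answers, so women who reported no intercourse can be credited with at-risk cycles

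*SAP*

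**What the plan says.** Under SAP 3.7.2, an extension cycle is at risk if the Cycle Contact form records intercourse and no backup contraception, or if the woman was pregnant in that cycle. The SAP says of this form that "this CRF wasn't present from the beginning of the study, but added as a mid-study change". The Protocol Revision History dates the change to version 5.0 (19 September 2017): "Added subject contact at the end of each 28-day cycle post the 52 Week visit". The same entry reads "Updated the potential risks / adverse events with PhII 1-year data", so first-year data from this study already existed.

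For cycles with no Cycle Contact information and no pregnancy, Step A counts the woman's missing cycles. Step B tells the analyst to "find proportion of pregnancy-risk cycles from Year 1 diary data of the subject". Step C multiplies the two, rounds to one decimal and adds the result to the Year 2 and Year 3 denominators. The SAP also plans both analyses without this fill. Its table list has -Y2 and -Y3 (no fill) beside -Y2M and -Y3M (with fill), and it does not say which pair leads.

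SAP 3.8.10 lists three questions from the long-term follow-up visits: any intercourse since the last visit, any additional birth control in the past 6 months, and "How often has the subject had vaginal intercourse in the past 6 months", whose lowest category is 'Not Once'. The only stated use is a categorical summary.

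**The concern.** After Week 52 no diary is collected, so Cycle Contact is the only cycle-by-cycle record of exposure. Where it is missing, the plan carries forward behaviour from an earlier year and does not check it against what the woman later said about the same months. SAP 3.7.1 and 3.7.2 both treat a cycle without intercourse as not at risk unless she became pregnant in it. An answer of no intercourse over the interval settles the matter for every cycle in it, yet the fill still credits exposure. The opposite error is also possible: a woman who used backup often in Year 1 and not at all since is under-credited.

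At stake is the denominator of the 2- and 3-year Pearl Index, which Protocol 20.6 names as a secondary analysis.

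**Working it through.** **The plan's own figure.** The only at-risk denominator stated is 2,015 cycles at 12 months for ages 18-35. From the protocol's sample size inputs: 225 × 10 × (1 − 0.01) × (1 − 0.092) = 2,022.6, within 0.4% of 2,015. The documents give no number of continuing women, missing cycles, extension pregnancies or 6-month answers, so everything below is illustrative.

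**One woman, 6 missing cycles.** Credited exposure = 6 × Year 1 proportion.
- Proportion 10/13: 4.6 cycles.
- Proportion 13/13: 6.0 cycles.
- A 6-month answer of 'Not Once' implies 0 in either case.
- Frequent intercourse with no additional method implies about 6.

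**2-year Pearl Index.** Assumptions: 2,015 Year 1 cycles, 130 continuers, 13 Year 2 cycles each, Year 1 proportion 0.9, all Year 2 cycles filled, 2 pregnancies by Cycle 26. Filled exposure = 130 × 13 × 0.9 = 1,521. Index = 2 × 1300 / L.

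| Case | L | Index |
|---|---|---|
| As filled | 2,015 + 1,521 = 3,536 | 0.74 |
| 5% of filled exposure not at risk | 2,015 + 1,444.95 = 3,459.95 | 0.75 |
| 20% not at risk | 2,015 + 1,216.8 = 3,231.8 | 0.80 |
| Every filled cycle at risk | 2,015 + 1,690 = 3,705 | 0.70 |
| Missing cycles dropped, none recorded | 2,015 | 1.29 |
| Missing cycles dropped, 23% recorded | 2,015 + 349.8 = 2,364.8 | 1.10 |

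SAP 3.7.1 exact interval for n = 2: limits on the count are χ²(0.025; 4)/2 = 0.242 and χ²(0.975; 6)/2 = 7.225. Multiplied by 1300/3,536 they give 0.09 to 2.66. At L = 3,231.8 they give 0.10 to 2.91.

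**3-year Pearl Index.** Assumptions: 100 continuers, 80% of 26 extension cycles in use (2,080), half of them missing, 3 pregnancies. Recorded at-risk cycles = 1,040 × 0.908 = 944.3, so L without the missing cycles = 2,959.3. Index = 3 × 1300 / L.
- SAP fill at 0.908: L = 3,903.6, index 1.00 (0.21, 2.92).
- True at-risk share of missing cycles 0.5: L = 3,479.3, index 1.12 (0.23, 3.28).
- True share 1.0: L = 3,999.3, index 0.98 (0.20, 2.85).
- Missing cycles dropped: index 1.32 (0.27, 3.85).

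**How many Year 2 cycles could lack a record.** Assumption: placements from 10 July to 31 December 2015, after protocol version 4.0. Study day on 19 September 2017 runs from 803 down to 629. Completed Year 2 cycles = (day − 364)/28, rounded down and capped at 13, which gives 13 down to 9. A placement on 1 June 2016 (day 476) gives 4. For Year 3, the earliest of these placements had completed (803 − 728)/28, or 2 cycles. On these dates the gap falls mainly in Year 2.

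**The case against.** The SAP discloses the late form and already plans the analysis both ways. The no-fill tables drop event-free cycles while keeping every pregnancy, so they push the index up. In the 2-year example, 0.74 and 1.10-1.29 bracket the 0.75-0.80 obtained when part of the filled exposure was not at risk. The Kaplan-Meier analyses do not use Steps A-C. The study is exploratory and this is a secondary analysis. Entry criteria (coitus expected at least monthly, a steady relationship) make 'Not Once' probably uncommon, at least at first. All of this stands, and it limits the weight of the point. It does not explain why an answer that settles the question should be ignored.

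A reader might infer three stronger things that the documents do not support.

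- *That neither version of the 2-year index is usable.* Within the filled version the assumed shifts are small against the interval.
- *That most Year 2 exposure certainly rests on the fill and that 6-month answers exist to replace it.* Enrolment dates and missing-cycle counts are not given. Nothing shows that the three questions were asked at visits before version 5.0: the SAP was written against eCRFs dated 30 January 2018.
- *That the 6-month answers should replace the fill throughout.* They cover an interval, and a report of additional birth control does not show which cycles it affected. Raising frequent, no-backup women to full exposure while leaving backup users on their Year 1 proportion is one-sided. Suppose 20% of women use backup and are at risk in half their cycles, the rest are always at risk, and every Year 1 proportion is 0.9. The true share is 0.8 × 1 + 0.2 × 0.5 = 0.90 (index 0.735, the same as the SAP fill). The one-sided rule credits 0.8 × 1 + 0.2 × 0.9 = 0.98, so L = 2,015 + 1,690 × 0.98 = 3,671.2 and the index falls to 0.708, in the device's favour.

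**Conclusion.** The point holds in limited form. As written, SAP 3.7.2 can credit at-risk cycles to a woman whose own follow-up answer says there were none, against the SAP's definition of an at-risk cycle. It affects Tables 14.2.1-Y2M and -Y3M only. The 1-year primary analysis, the no-fill tables and the Kaplan-Meier analyses do not use the fill.

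The direction of bias cannot be determined. Year 1 behaviour may overstate or understate later risk. Step B may also understate it: SAP 3.7.1 excludes Year 1 cycles with a day lacking backup information, but those cycles may stay in the Step B total. The size is probably modest: on the assumed 2-year inputs, a change from 0.74 to between 0.70 and 0.80. That range rests on assumed numbers of continuers, pregnancies and missing cycles, and on all Year 2 cycles being filled.

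**What to change.** In SAP 3.7.2, insert one step before Steps A-C. A cycle without Cycle Contact data and without a pregnancy is set to not at risk when the 6-month form covering it reports no intercourse since the last visit, or 'Not Once' in the past 6 months. All other or missing answers stay with Steps A-C, so the rule does no harm where the questions were not asked.

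Add a sensitivity analysis that treats both directions alike:
- Intervals with frequent intercourse and no additional method are set to at risk.
- Intervals with additional birth control reported are bounded by setting their missing cycles first to 0 and then to 1.

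Report the number of denominator cycles from each source: Cycle Contact, 6-month answer and Year 1 fill.

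The cost is a short SAP insertion and a small amount of programming to merge a form the SAP already summarises. The downside is that a 6-month recall is coarser than a per-cycle record. For that reason only the no-intercourse answer enters the main filled version.

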## 3.7 Efficacy Analyses

## 3.7.1 Efficacy Analyses for Year 1 Data

Primary efficacy analysis was performed for the first year of the study (through Day 364) for Evaluable for Pregnancy population, by using Pearl Index. Pearl Index is defined as the number of pregnancies in 100 woman-years of method use. Pearl Index was calculated in subjects aged 18-35 at the time of VeraCept placement through the date of VeraCept removal or pregnancy, excluding the following cycles, unless the subject became pregnant in that cycle:

- When back-up contraception use was documented on the daily diary
- When the subject had no intercourse.

The Pearl Index formula is:

$$r = \frac{n}{L} \times 1300 = \frac{\text{Number of pregnancies}}{\text{Number of woman-cycles of pregnancy-risk}} \times 1300$$

where n is the number of pregnancies, and L is the number of woman-cycles, i.e., sum of the number of cycles each woman used the VeraCept up to and including the cycle of conception or until the time of VeraCept removal/expulsion, whichever comes earlier. The cycles of pregnancy-risk will be calculated as (Date of VeraCept removal/expulsion – Date of VeraCept placement + 1) / 28 for women who are not pregnant, and as (Date of pregnancy – Date of VeraCept placement + 1) / 28 for women who became pregnant

during the study. On-treatment pregnancies are defined to be pregnancies for which the estimated date of conception was within 7 days after study device expulsion or removal (the earlier of expulsion and removal dates will be used). The last cycle of pregnancy-risk can be a partial cycle and the partial cycle at risk is determined by dividing the number of days at risk in the cycle by 28 (e.g., 14/28 = 0.5 cycle of risk). If a cycle has a day with no information about backup contraception, that cycle will be excluded from the analysis (unless the subject became pregnant in that cycle).

To get the confidence interval (CI) for the Pearl Index, first the CI for the n (number of pregnancies) will be approximated by Poisson distribution sample mean's CI as

$$(\frac{\chi^{2}(\alpha/2;2n)}{2},\frac{\chi^{2}(1-\alpha/2;2n+2)}{2})$$

where  $\chi^2(\alpha/2;2n)$  in the lower limit is the Chi-square distribution (degrees of freedom = 2n) percentile with lower tail area (probability)  $\alpha/2$ , and  $\chi^2(1-\alpha/2;2n+2)$  in the upper limit is similarly defined. If n = 0, the lower limit will be set as 0.

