Then the 95% CI for Pearl Index will be estimated as follows by set  $\alpha = 0.05$ .

( 
$$\frac{\chi^2(\alpha/2;2n)}{2}$$
 / L x 1300,  $\frac{\chi^2(1-\alpha/2;2n+2)}{2}$  / L x 1300 )

The summary table will present the number of subjects in the EP analysis population, number of pregnancies and the number of cycles of risk in addition to the Pearl Index and its 95% CI, for the following 3 scenarios:

- All EP subjects
- EP subjects with at least one live birth
- EP subjects never had live birth

Life-Table (Kaplan-Meier) method will also be used to present probabilities of pregnancy through 1-year (13 cycles) interval (through Day 364). The Evaluable for Pregnancy population will be used for the analysis and cycles will be compressed to provide contiguous cycles.

All efficacy analyses will be first done for all EP population, and then done by parity for 2 sub-groups of EP population: one sub-group subjects who had live child birth, and the other sub-group subjects who had not.

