14.1.10.4	List of Medications Used by Subjects who Failed the Insertion Procedure	ITT
14.2.1-Y1	1-Year Pearl Index	EP
14.2.1-Y2	2-Year Pearl Index - No Missing Cycle Contact	EP
14.2.1-Y2M	2-Year Pearl Index – with Estimation for Missing Cycle Contact	EP
14.2.1-Y3	3-Year Pearl Index – No Missing Cycle Contact	EP
14.2.1-Y3M	3-Year Pearl Index – with Estimation for Missing Cycle Contact	EP
14.3.0	Treatment Exposure	Safety
14.3.0T	Treatment Exposure	ITT
14.3.1.1	Overall Number and Percentage of Subjects with Adverse Events	Safety
14.3.1.1T	Overall Number and Percentage of Subjects with Adverse Events	ITT
14.3.1.2	Overall Number of Adverse Events by Severity and Relatedness to the Study Product	Safety
14.3.1.2T	Overall Number of Adverse Events by Severity and Relatedness to the Study Product	ITT
14.3.1.3C	Summary of Adverse Events by System Organ Class in Descending Order of Frequencies	Safety
14.3.1.3P	Summary of Adverse Events by Preferred Term in Descending Order of Frequencies	Safety

14.3.1.3P-Y1	Summary of Year 1 Adverse Events by Preferred	Safety
	Term in Descending Order of Frequencies	
14.3.1.3P-Y2	Summary of Year 2 Adverse Events by Preferred Term in Descending Order of Frequencies	Safety
14.3.1.3P-Y3	Summary of Year 3 Adverse Events by Preferred Term in Descending Order of Frequencies	Safety
14.3.1.4	Summary of Adverse Events by System Organ Class and Preferred Term	Safety
14.3.1.4T	Summary of Adverse Events by System Organ Class and Preferred Term	ITT
14.3.1.5	Summary of Serious Adverse Events by System Organ Class and Preferred Term	Safety
14.3.1.6	Summary of Adverse Events that Led to Premature Study Discontinuation	Safety
14.3.1.7C	Summary of Adverse Events by System Organ Class and by Severity	Safety
14.3.1.7	Summary of Adverse Events by System Organ Class and Preferred Term and by Severity	Safety
14.3.1.8C	Summary of Adverse Events by System Organ Class and by Relatedness to the Study Product	Safety
14.3.1.8	Summary of Adverse Events by System Organ Class and Preferred Term and by Relatedness to the Study Product	Safety
14.3.1.9A	Summary of Allergy-Related Symptoms by Onset Time	Safety
14.3.1.9B	Summary of Dyspareunia by Onset Time	Safety
14.3.2.1	List of Serious Adverse Events	Safety
14.3.2.2	List of Adverse Events that Led to Premature Study Discontinuation	Safety
14.3.5	Device Placement and Subject Pain During the Procedure	Safety
14.3.6	Device Expulsion or Removal and Subject Pain During the Procedure	Safety

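### The No Missing Cycle Contact Pearl Indices at 2 and 3 years keep every on-treatment pregnancy but drop event-free extension cycles without contact data, so they are biased upward in expectation

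*SAP*

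**What the plan says.** SAP 3.7.2 takes post-Year 1 information on intercourse and back-up use from the Cycle Contact form, and notes that "this CRF wasn't present from the beginning of the study, but added as a mid-study change". Three rules then apply.

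- A cycle in which the woman became pregnant is a pregnancy-risk cycle whether or not a contact was recorded.
- A cycle is treated as missing when neither contact question was answered and the woman was not pregnant in it. Steps A to C estimate how many of these were at risk from her own Year 1 diary.
- On the event count: "The numerator will be the number of on-treatment pregnancies by the end of Cycle 26 and Cycle 39, respectively".

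A second version skips Steps A to C: "The Year 2 and Year 3 analyses will also be performed without inclusion of cycles with missing Cycle Contact information". SAP 5.2 lists it as Tables 14.2.1-Y2 ("2-Year Pearl Index - No Missing Cycle Contact") and 14.2.1-Y3, beside the estimated Tables -Y2M and -Y3M.

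The revision history at the front of the protocol dates the contact to Version 5.0, 19 September 2017: "Added subject contact at the end of each 28-day cycle post the 52 Week visit". The same entry says: "Updated the potential risks / adverse events with PhII 1-year data".

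**The concern.** Dropping the missing cycles removes only event-free time, while the numerator is untouched. Where no form existed, a cycle counts if the woman conceived in it and otherwise disappears. Numerator and denominator then cover different periods.

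The two versions are the only pair in the plan that shows how far the 2- and 3-year indices depend on imputing from Year 1 behaviour. A gap between them would contain this mismatch as well as any effect of the imputation. The SAP does not state the direction of the bias, does not explicitly name a lead version, and does not ask for the number of pregnancies conceived in cycles without contact data. A reader could take the higher figure as evidence about the device in Years 2 and 3 when part of it reflects the date a form was introduced.

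**Working it through.** **The plan's own figure.** The documents give no 2- or 3-year Pearl Index. The only stated one is for 12 months: 1 pregnancy in 2,015 cycles (SAP 2.5). SAP 3.7.1 sets the index at n / L x 1300, where "L is the number of woman-cycles, i.e., sum of the number of cycles each woman used the VeraCept". So 1 x 1300 / 2,015 = 0.645, which agrees with the stated 0.6. The SAP's chi-square limits give (0.02, 3.60), not the stated (0.1, 3.3). That is a separate matter and does not affect this point.

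**Direction.** Let L_c be the at-risk cycles that are counted and L_m the estimated at-risk cycles among the missing ones.

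- Estimated version: n x 1300 / (L_c + L_m).
- No Missing version: n x 1300 / L_c.
- Ratio: (L_c + L_m) / L_c, which is at least 1 whenever n is 1 or more.

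**Is there pre-form extension time?** Protocol Table 1 dispenses no diary after Visit 5, so the Year 1 source does not continue. Version 5.0 introduced the contact and already carried first-year results (Protocol 6.2). Its revision entry also describes separating out the period from week 52 to Year 3 for clarity, which suggests that follow-up past week 52 was already planned. This supports some extension use before the form, but no passage counts it.

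**Size at 2 years (illustration).** Inputs from the documents: 2,015 Year 1 cycles, 225 women aged 18-35, 13 cycles per year, and 9.2% of cycles not at risk (share at risk 0.908). Assumed: 60% of women continue, 90% of the 13 extension cycles are used, and a share m of extension at-risk cycles has no contact data.

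Extension at-risk cycles: 225 x 0.60 x 13 x 0.9 x 0.908 = 1,434.

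L = 2,015 + (1 - m) x 1,434

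| m | L | Ratio to m = 0 | Index, n = 2 |
|---|---|---|---|
| 0 | 3,449 | 1.00 | 0.75 |
| 20% | 3,162 | 1.09 | 0.82 |
| 50% | 2,732 | 1.26 | 0.95 |
| 80% | 2,302 | 1.50 | 1.13 |

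**Range.** A second set of assumptions uses 225 x 0.99 women, 50% to 90% continuing through the extension, all cycles used, and 10% to 75% of extension cycles missing. The ratio is then 1.04 to 1.68 at Year 2 and 1.06 to 2.11 at Year 3.

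**What the asymmetry contributes.** The table above fixes n = 2 without saying when conception occurred, so it does not isolate the mismatch. Take m = 50% and treat all missing cycles as pre-form.

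- Both pregnancies in Year 1 or in covered extension cycles: No Missing gives 2 x 1300 / 2,732 = 0.95. A rule applied equally to numerator and denominator also gives 0.95.
- One of the two in pre-form time: No Missing gives 2 x 1300 / 2,733 = 0.95. The symmetric rule gives 1 x 1300 / 2,732 = 0.48. The estimated version gives 0.75 in both cases.

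The bias is therefore a matter of expectation. A Poisson simulation at a true index of 0.6 (Year 2, 70% continuing, second set of assumptions) gave mean No Missing indices of 0.68, 0.79 and 0.94 with 25%, 50% and 75% missing. The estimated version, with its denominator set to the true at-risk cycles, and the symmetric version each averaged 0.60.

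**No pregnancies.** The index is 0 in both versions. The upper limit is 3.689 x 1300 / L, where 3.689 is half the 97.5% chi-square point on 2 degrees of freedom. It rises from 1.39 (L = 3,449) to 1.76 (L = 2,732).

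**The case against.** The best defence is consistency. In Year 1, SAP 3.7.1 already excludes a cycle that has a day without back-up information unless the woman conceived in that cycle. The Year 2 and 3 version extends that rule. This stands: a reader might infer a departure from the plan's own convention, and the documents do not support that. What differs is the possible scale. The Year 1 rule removes individual cycles while the diary was in use; here a whole administrative block may go.

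A reader might also state as fact that coverage before the form was zero. The SAP's remark that the form was added since the extension started can be read as leaving little such time, and nothing rules out retrospective completion. The gap is an inference with unknown size.

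Nor do the documents support calling the comparison uninterpretable. Both versions share a numerator, so their ratio is the ratio of denominators and its direction is known. The estimated tables stand alongside, and the Kaplan-Meier analyses in SAP 3.7.2 have no stated dependence on contact answers. In the n = 2 illustration the intervals are wide: 0.75 (0.09, 2.72) against 0.95 (0.12, 3.44). Overlap does not remove a systematic shift, but it keeps its importance in proportion.

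Finally, excluding real failures from a contraceptive table would be a poor remedy on its own. That is right, and the all-pregnancy figure should remain.

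**Conclusion.** The point holds as an upward bias in expectation in Tables 14.2.1-Y2 and -Y3. With at least one pregnancy, the No Missing index is never below the estimated one. It is tempting to say that the failure rate is overstated by construction. The documents do not support that: if no pregnancy is conceived in a cycle without contact data, the index equals a symmetric complete-case index.

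The 2-year inflation of about 1.1 to 1.5 times rests on assumed values for continuation, cycles used and missing contacts; the documents give none of them. The consequence is limited. SAP 3.1.2 makes the 1-year analysis the main one, the study is exploratory, and no decision rule uses these tables. A correction is still worth making because it is cheap and the SAP does not warn of the direction.

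**What to change.** In Tables 14.2.1-Y2 and -Y3:

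- Add a row in which each woman's extension risk period starts at the first 28-day cycle for which the Cycle Contact form was in use at her site. Apply that start to pregnancies and cycles alike, and leave Year 1 unchanged. The date is administrative and unrelated to outcome.
- Keep the all-pregnancy row and label it as a conservative upper figure, so that no failure leaves the table.
- Report the number of dropped cycles and the number of pregnancies conceived in cycles without Cycle Contact data.
- State that contacts missed after the form was in use still follow the existing rule of exclusion unless pregnant. The added row does not remove that smaller asymmetry.

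The cost is SAP wording, a form-in-use date per site, and less extension time in the added row, which may show fewer pregnancies than the row beside it. Tables -Y2M and -Y3M need no change.
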